#### 4.10.7 Concomitant Medications

Concomitant medications will be coded with WHODrug (Global March 2019) using the WHODrug Insight tool. Each codable concomitant medication will be assigned five values: Drug Name, Drug Record Number, SeqNum1, SeqNum 2, and Anatomic Therapeutic Class (ATC) code. Results will be tabulated by treatment group, ATC code, and Drug Name during the Randomization and Extension Phases, separately. Note that all concomitant medications with a given Drug Record Number will be assigned the same ATC code.

Unless the start date of the medication is after the last study drug dose date, or the end date of the medication is prior to the start date of the study drug, the medication will be considered 'concomitant.' Partial onset and dates need to be considered in the determination of the medication being concomitant or not.

#### 4.10.8 Sheehan-Suicidality Tracking Scale (S-STS)

The S-STS is a prospective, self-reported rating scale that contains 16 questions to track both treatment-emergent suicidal ideation and behaviors. In the event the participant is unavailable, the S-STS clinician-administered rating scale with 6 yes/no questions will be completed.

Self-reported S-STS scores are calculated as follows:

- Ideation subscale score: Sum of scores (0-4) for Questions 2-11
- Behavior subscale score: Sum of scores (0 4) for Questions 1a, (highest of 12 or any row of 16), (highest of 14 or any row of 15), 17, and 20 based on the scoring used for the 2017 version of scale used in this study. In addition, a Behavior subscale score based on the 2019 version of the scoring will also be calculated where the score for a 'Yes' item 20 is 56 and the scores for 18, 19, 21 and 22 are used from the prior visit if applicable.
- Total score: Sum of the ideation and behavior subscale scores. A Total score will be calculated based on both 2017 version and 2019 version

The self-reported S-STS ideation subscale, behavior subscale, and total score will be summarized as the change from baseline (i.e., <-1, -1, no change, 1, >1) at each visit and at Maximum score in the Randomization and Extension Phases, presented separately. Both

versions of the Total score will be summarized. All S-STS assessments will be included in summaries regardless of being completed at study site or remote.

#### 4.10.9 Subjects Identified for Narratives

A safety narrative will be prepared for each subject who received at least one dose of troriluzole and experienced the following events (regardless of relationship to study drug) on-treatment with Troriluzole:

- All deaths on-treatment and post-treatment through the end of the study
- SAEs on-treatment, which includes up to 30 days after the last dose of study drug; SAEs that occur > 30 days (i.e., during the follow-up period) will be included per the clinical judgment of the Biohaven medical monitor
- All premature discontinuations of study drug due to AEs (either identified through "action taken" or "end of treatment status")
- The following on-treatment events of special interest:
  - Neutropenia based on laboratory results and defined as minimum absolute neutrophil count < 500 per mm3

  - LFT abnormalities:
    - $\circ \quad \text{ALT or AST} > 3x \text{ ULN}$
    - ALT or AST > 3x ULN, and serum total bilirubin > 2x ULN

Interstitial lung disease Standardized MedDRA Query (SMQ) including eosinophilic pneumonia and hypersensitivity pneumonitis

These select events are described in the current version (v3) of the Biohaven Safety Narrative Scope for BHV-4157 (troriluzole). Because select events may be subject to change, updates to the list of events or selection algorithms after database lock may be described in a Note to File (NTF) rather than amending the SAP.

A by-subject listing of safety narrative subject identifiers will be presented for all troriluzole treated subjects with the select events as described above.

# APPENDIX

## **APPENDIX 1 - Study Plan and Procedures at Each Visit**

# Table 1: Schedule of Assessments and Events – Double-Blind Phase

Visit Number	1	2	3	4	5	6	7	8	9 or Early Term	10	
Study Visit Time Point	Screening (within 42 days prior to baseline)	Baseline (Week 0)	Week 2 (±3 days)	Week 4 (±7 days)	Week 8 (±7 days)	Week 12 (±7 days)	Week 24 (±7 days)	Week 36 (±7 days)	Week 48  (±7 days)	Follow-Up Week 52 (±7 days)	Unscheduled Visit 
Informed Consent	Х										
Eligibility Review	Х	Х									
Randomization 		Х									
Med History/Demographics	Х										
Modified Hachinski Ischemic Scale	Х										
Height  & Weight	Х	Х		Х	Х	Х	Х	Х	X	Х	
Physical Examination	Х	Х		Х	Х	Х	Х	Х	X	Х	
Neurological Examination	Х										
Vital Signs 	Х	Х		Х	Х	Х	Х	Х	X	Х	Х
Concomitant Medication	Х	Х	Х	Х	Х	Х	Х	Х	Х	Х	
Adverse Events 	Х	Х	Х	Х	Х	Х	Х	Х	Х	Х	Х
12-lead ECG (resting)	Х					Х	Х		X	Х	
Clinical Safety Blood Tests 	Х	Х		Х	Х	Х	Х	X 	Х	Х	
B12 (blood test)	Х										
Urinalysis 	Х	Х		Х		Х	Х		Х		
HIV, HBsAg, HCV antibody	Х										
ApoE4 (blood test)	Х										
Blood Collection for Biomarker Banking		Х					Х		х		
Blood Collection for Pharmacokinetics 		X		X	X	Х	Х		X		
Visit Number	1	2	3	4	5	6	7	8	9 or Early Term	10	

ADCS & Biohaven Pharmaceuticals Protocol BHV4157-203

#### Confidential 03DEC2020

Study Visit Time Point	Screening (within 42 days prior to baseline)	Baseline (Week 0)	Week 2 (±3 days)	Week 4 (±7 days)	Week 8 (±7 days)	Week 12 (±7 days)	Week 24 (±7 days)	Week 36 (±7 days)	Week 48 (±7 days)	Follow-Up week 52 (±7 days)	Unscheduled Visit
Volumetric MRI 	Х						Х		Х		
Lumbar Puncture (LP) 	Х						Х		Х		
CSF Biomarkers 	Х						Х		Х		
Post-LP Safety Telephone 	Х						Х		Х		
Sheehan Suicidality Tracking	Х	Х		Х	Х	Х	Х	Х	Х	Х	
ADAS-Cog 11		Х				Х	Х	Х	Х		
CDR-SOB		Х				Х	Х	Х	Х		
NPI		Х					Х		Х		
ADCS-ADL		Х					Х		Х		
Craft Story 21 Recall		Х							Х		
Benson Complex Figure		Х							Х		
MINT		Х							Х		
Letter & Category Fluency		Х							Х		
Trail Making Test A & B		Х							Х		
Number Span Test		Х							Х		
MMSE	Х	Х					Х		Х		
MoCA		Х					Х		Х		
Research Satisfaction Survey		Х				Х	Х	Х	Х		
Dispense Study Drug 		Х		Х	Х	Х	Х	Х			
Study Drug Instruction Phone Call 			Х								
Study Drug Accountability				Х	Х	Х	Х	Х	X		
Treatment Blinding Questionnaire 									Х		

Every effort should be made to conduct the Week 48 visit and maintain the +/- 7 day window. However, due to concerns related to the COVID-19 pandemic, the Week 48 visit window may be modified beyond the +/- 7 day window, in order to minimize any potential risks to study participant safety and to comply with governmental and local institutional guidance (e.g., study site has a policy that a clinical research visit must be delayed). Under these circumstances, the visit window may be extended (up to a maximum treatment duration of 60 weeks), but every attempt should be made to conduct the visit as close to the date the visit is due as possible. If the visit window is modified, participants should be evaluated remotely (e.g., via phone) at the time of the scheduled Week 48 visit to perform and document appropriate safety assessments. Study medication may be sent to the participant via tracked and certified courier. For any such cases, the investigator should discuss the specific circumstances of each case with the sponsor medical monitor (or designee) who must approve the request prior to any modification of the visit window: PPD Cell PPD

PPD

The following must be collected at any unscheduled visit: vital signs, prior and concomitant medications, adverse events, and protocol deviations. All other unscheduled visit procedures are subject to PI discretion or request from the Medical Monitor.

Confidential 03DEC2020

- 2 Randomization must occur at the baseline visit after eligibility is confirmed.
-  Height is done at screening only.
- 4 Vital signs include sitting blood pressure, pulse, temperature, respiration rate, and weight.
-  The SAE reporting period starts at the screening visit (i.e., when the participant or LAR signs consent). The reporting period for non-serious AEs starts at the baseline visit at the time of receiving the first dose of study drug. The end of the reporting period for both SAEs and AEs is 30 days after the study drug has been discontinued.
-  Clinical Safety Laboratory Tests will be performed by a Central Laboratory. Assessment includes the following: Hematology (hemoglobin, hematocrit, platelets, RBC, WBC, differential count, and absolute neutrophil count), Chemistry (sodium, potassium, chloride, calcium, ALT, AST, LDH, alkaline phosphatase, GGT, phosphorus, bicarbonate, CPK, total protein, albumin, indirect bilirubin, direct bilirubin, total bilirubin, glucose, creatinine, BUN, uric acid, total cholesterol, LDL, HDL, triglycerides, folate).
- 7 Performing additional safety labs at Week 36 is now strongly encouraged, given the COVID-19 pandemic and unanticipated issues related to collecting lab samples that may potentially arise.
-  Urinalysis to include: pH, specific gravity, protein, glucose, ketones, urobilinogen, bilirubin, blood
- A blood sample for pharmacokinetic (PK) measures in plasma should be collected at baseline, week 4, week 8, week 12, week 24, and week 48. Participants should take their dose at their routine time on the days of these visits. Date and time of last dose should be collected in case report forms for entry into the EDC system. Participants who are able scheduled for a morning visit should be instructed to hold their dose of study drug that morning until after a PK trough sample is obtained, if possible and appropriate in the judgment of the investigator. Blood samples for PK in plasma should be drawn if there are any SAEs that could possibly be drug-related or severe AEs that could be drug-related. In addition, for participants that are undergoing lumbar puncture, PK samples should be drawn at the time of lumbar puncture. Date and time of doses on the day of lumbar puncture and day prior should be collected in case report forms, for entry into the EDC system.
-  All vMRIs must be performed per imaging protocol and must use the same scanner throughout study.
  - Screening vMRI: if a participant has not had an MRI performed within 6 months of screening (i.e., within 6 months from the date of informed consent), then an MRI must be performed as part of the screening requirements for this study, per the imaging protocol, and should be one of the last screening procedures performed to determine final eligibility in order to prevent participants from undergoing unnecessary MRIs. If a participant has had an MRI within 6 months of screening (i.e., within 6 months from the date of informed consent) but the MRI does not follow the study-specific imaging protocol, that MRI can be used to help determine eligibility; however, another MRI must be performed per the imaging protocol, and must occur as close to, and prior to, the baseline visit, after all other eligibility criteria have been confirmed.
  - Week 24 and week 48 vMRI: the protocol window for vMRI at week 24 and week 48 is 14 days before and up to 14 days after the clinic visit. If participant is terminating early at 36 week or after, obtain vMRI. If MRI is performed on the same day as a lumbar puncture at week 48, the vMRI must be conducted before the lumbar puncture. Otherwise, at least a 3-day window between vMRI and the lumbar puncture is required.
- It is anticipated that lumbar puncture will be performed on an estimated 100 study participants as part of a sub-study (separate informed consent required).
- Only for the CSF sub-study. Visit windows for CSF are: up to 14 days prior to first dose of study medication and up to 14 days prior to weeks 24 and 48. If a participant in the CSF sub-study is terminating early, they do not need to undergo lumbar puncture.
-  Post lumbar puncture safety follow up telephone call must occur 1 to 3 days after the lumbar puncture is performed.
-  First dose of study medication will be given in the clinic at the baseline clinic visit after completion of the baseline visit procedures.
-  Participants will receive a phone call during Week 2 from site study personnel in order to assess study drug tolerability. If tolerable, then the participant will be instructed to proceed with dose escalation.
-  Treatment blinding questionnaire to be administered to site PI and Raters.

# Table 2: Schedule of Assessments and Events – Open-Label Extension Phase

Visit Number	1	2	3	4	5	6	7	8	9	10	
Study Visit Timepoint	Baseline 	Abbrev- iated Drug Dispensat ion Visit 	Ext Week 2 (+/- 7 days)	Ext Week 4 (+/- 7 days)	Ext Week 8  (+/- 7 days)	Ext Week 12 (+/- 7 days)	Ext Week 24 (+/- 7 days)	Ext Week 36 (+/- 7 days)	Ext Week 48 or Early Term (+/- 7 days)	Week2 Post last dose (+/- 7 days)	Unsched- uled Visit  (+/- 7 days)
Informed Consent	Х	Х									
Medical History	Х										
Adverse Event Assessment	Х	Х	Х	Х	X 	Х	Х	Х	Х	Х	
Telephone Check-in  Includes AE assessment and concomitant medication review			Х		X 						
Laboratory Assessments 	Х			Х	X 	Х	Х	Х	Х		
Urinalysis	Х						Х		Х		
Physical Exam	Х								Х		
Physical Measurement - Weight	Х						Х		Х		
Vital Signs	Х	Х		Х		Х	Х	Х	Х	Х	Х
12-Lead ECG	Х					Х	Х		Х		
Concomitant Medication Review	Х	Х	Х	Х	Х	Х	Х	Х	Х	Х	Х
Sheehan Suicidality Tracking Scale (S-STS)	Х	Х		Х		Х	Х	Х	Х	Х	
Dispense Study Drug	Х	Х		Х		Х	Х	Х			
Volumetric MRI 	Х								Х		
ADAS-Cog 11	Х						Х		Х		
CDR-SOB	Х						Х		Х		
Study Drug Accountability				Х		Х	Х	Х	Х		
Blood Collection for Biomarker											
Banking							Х		Х		
Craft Story 21 Recall	Х						Х		Х		
Letter & Category Fluency	Х						Х		Х		
Number Span Test	Х						Х		Х		
MoCA	X						X		X		

ADCS & Biohaven Pharmaceuticals Protocol BHV4157-203 Confidential 03DEC2020

- 1. Baseline visit for the Extension Phase is only required if there is an extended break (≥4 weeks) in dosing between the Randomization and Extension Phases.
- 2. For participants who will have been off of the study drug for less than or equal to 4 weeks, the subject should come into the investigative site for an Abbreviated Drug Dispensation Visit (also "Abbreviated OLE Baseline Visit"), at which time any major medical or medications changes will be reviewed prior to dispensing riluzole. In this case, most procedures from the Week 48 visit will also serve as the Open-Label Extension Phase Baseline visit
- 3. Extension Week 8 is primarily to collect Liver Function tests. If a participant prefers not to come into the office, these can be collected at a local laboratory, with a telephone call confirming these were collected as well as a review of concomitant medications and an assessment of any adverse events. If the participant comes into the center, an assessment of adverse events and Liver function tests will be completed. Although all other visits can be conducted remotely as needed due to COVID-19 restrictions, under regular circumstances visits are to be completed in-person. See Protocol Section 8.1.12, Open-Label Extension Phase, for further details and requirements regarding remote visit completion due to COVID-19.
- 4. The following must be collected at any unscheduled visit: vital signs, prior and concomitant medications, adverse events, and protocol deviations. All other unscheduled visit procedures are subject to PI discretion or request from the Medical Monitor.
- 5. Telephone calls to subjects will be made between visits during Extension Phase (Weeks 2 and 8) to monitor subject condition, review concomitant medications and assess any adverse events.
- 6. Clinical Safety Laboratory Tests will be performed by a Central Laboratory. Assessment includes the following: Hematology (hemoglobin, hematocrit, platelets, RBC, WBC, differential count, and absolute neutrophil count), Chemistry (sodium, potassium, chloride, calcium, ALT, AST, LDH, alkaline phosphatase, GGT, phosphorus, bicarbonate, CPK, total protein, albumin, indirect bilirubin, direct bilirubin, total bilirubin, glucose, creatinine, BUN, uric acid, folate).
- 7. Volumetric MRI is not required if the participant's Double-Blind Week 48 MRI scan occurred less than than 3 months prior to their joining the Open-Label Extension Phase.

#### Table 2: Schedule of Assessments and Events – Open-Label Extension Phase

Visit Number	1	2	3	4	5	6	7	8	9	10	
Study Visit Timepoint	Baseline 	Abbrev- iated Drug Dispensat ion Visit 	Ext Week 2 (+/- 7 days)	Ext Week 4 (+/- 7 days)	Ext Week 8  (+/- 7 days)	Ext Week 12 (+/- 7 days)	Ext Week 24 (+/- 7 days)	Ext Week 36 (+/- 7 days)	Ext Week 48 or Early Term (+/- 7 days)	Week2 Post last dose (+/- 7 days)	Unsched- uled Visit  (+/- 7 days)
Informed Consent	X	X									
Medical History	X										
Adverse Event Assessment	X	X	X	X	X 	Х	Х	Х	Х	Х	
Telephone Check-in  Includes AE assessment and concomitant medication review			Х		X 						
Laboratory Assessments 	Х			Х	$X^3$	Х	Х	Х	Х		
Urinalysis	Х						Х		Х		
Physical Exam	Х								Х		
Physical Measurement - Weight	Х						Х		Х		
Vital Signs	Х	Х		Х		Х	Х	Х	Х	Х	Х
12-Lead ECG	Х					Х	Х		Х		
Concomitant Medication Review	Х	Х	Х	Х	Х	Х	Х	Х	Х	Х	Х
Sheehan Suicidality Tracking	Х	Х		Х		Х	Х	Х	Х	Х	
Scale (S-STS)											
Dispense Study Drug	Х	Х		Х		Х	Х	Х			
Volumetric MRI 	Х								Х		
ADAS-Cog 11	Х						Х		Х		
CDR-SOB	Х						Х		Х		
Study Drug Accountability				Х		Х	Х	Х	Х		
Blood Collection for Biomarker											
Banking							Х		Х		
Craft Story 21 Recall	Х						Х		Х		
Letter & Category Fluency	Х						Х		Х		
Number Span Test	Х						Х		Х		
MoCA	X						X		X		

8. Baseline visit for the Extension Phase is only required if there is an extended break (≥4 weeks) in dosing between the Randomization and Extension Phases.

ADCS & Biohaven Pharmaceuticals Protocol BHV4157-203 Confidential 03DEC2020

- 9. For participants who will have been off of the study drug for less than or equal to 4 weeks, the subject should come into the investigative site for an Abbreviated Drug Dispensation Visit (also "Abbreviated OLE Baseline Visit"), at which time any major medical or medications changes will be reviewed prior to dispensing riluzole. In this case, most procedures from the Week 48 visit will also serve as the Open-Label Extension Phase Baseline visit
- 10. Extension Week 8 is primarily to collect Liver Function tests. If a participant prefers not to come into the office, these can be collected at a local laboratory, with a telephone call confirming these were collected as well as a review of concomitant medications and an assessment of any adverse events. If the participant comes into the center, an assessment of adverse events and Liver function tests will be completed. Although all other visits can be conducted remotely as needed due to COVID-19 restrictions, under regular circumstances visits are to be completed in-person. See Protocol Section 8.1.12, Open-Label Extension Phase, for further details and requirements regarding remote visit completion due to COVID-19.
- 11. The following must be collected at any unscheduled visit: vital signs, prior and concomitant medications, adverse events, and protocol deviations. All other unscheduled visit procedures are subject to PI discretion or request from the Medical Monitor.
- 12. Telephone calls to subjects will be made between visits during Extension Phase (Weeks 2 and 8) to monitor subject condition, review concomitant medications and assess any adverse events.
- 13. Clinical Safety Laboratory Tests will be performed by a Central Laboratory. Assessment includes the following: Hematology (hemoglobin, hematocrit, platelets, RBC, WBC, differential count, and absolute neutrophil count), Chemistry (sodium, potassium, chloride, calcium, ALT, AST, LDH, alkaline phosphatase, GGT, phosphorus, bicarbonate, CPK, total protein, albumin, indirect bilirubin, direct bilirubin, total bilirubin, glucose, creatinine, BUN, uric acid, folate).
- 14. Volumetric MRI is not required if the participant's Double-Blind Week 48 MRI scan occurred less than than 3 months prior to their joining the Open-Label Extension Phase.

# APPENDIX 2 - Calculating the ADAS-Cog Total Score when there are missing data

The ADAS-Cog is a rater-administered scale with eight performance subtests: Word Recall; Commands; Constructional Praxis; Naming; Ideational Praxis; Orientation; Word Recognition; Remembering Word Recognition Test Instructions. Three examiner ratings, of Spoken Language, Language Comprehension, and Word Finding Difficulty, also are obtained. The test is scored in terms of errors, with higher scores reflecting poorer performance and greater impairment. Scores can range from 0 (best) to 70 (worst).

If a participant is unable to complete any of the eight performance subtests, the rater must code the reason for incompletion:

- Not done for reasons other than physical or cognitive
- Participant refused
- - Participant unable to complete for physical reasons
- - Participant unable to complete for cognitive reasons

When total scores for performance subtest measures are missing because the participant is unable to complete the task for cognitive reasons, the worst possible score for the measure will be assigned.

Because Remembering Test Instructions is scored solely based on performance on Word Recognition, if Word Recognition was not completed for any reason, then Remembering Test Instructions must also be scored as not completed.

#### For a given individual performance subtest:

If 25% or fewer of the items within a subtest are missing, scores for the missing items will be prorated as the average of the completed items on that subtest. This procedure will be employed for a maximum of two performance subtests.

If more than 25% of the items within any performance subtest are missing, the entire subtest is missing.

#### For the ADAS-Cog Total Score

The total score is the sum of 11 subscales (8 performance subtests and 3 examiner ratings). If more than two subscales (either performance subtest or examiner ratings) are missing or more than 2 performance subtests have partial missing data or if both the Word Recall and Word Recognition subtests are missing, then the ADAS-Cog total score will be missing. Otherwise, the total score will be based on the sum of the scores from the non-missing subscales multiplied (prorated) by the ratio (max ADAS-cog Total Score of 70/max total possible from non-missing subscales).

ADCS & Biohaven Pharmaceuticals Protocol BHV4157-203

For example, if the Word Recall performance subtest , which ranges from 0-10 (maximum=10), is missing, and another subtest Commands, which ranges from a score of 0-5 (maximum = 5) is also missing, then the total ADAS-cog score will be calculated as the sum from the 9 non-missing subscales multiplied by the ratio (70/(70 - (10 + 5)) = 70/55 = 1.27), the resulting prorated total score will be rounded up to the nearest integer

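### SAP Appendix 2 gives no ADAS-Cog 11 total when three subtests are each partly missing, yet gives one when one of those three is not done at all

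*SAP*

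**What the plan says.** SAP Appendix 2 works at two levels.

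Within a performance subtest, small gaps are filled: "If 25% or fewer of the items within a subtest are missing, scores for the missing items will be prorated" from the completed items. There is a cap: "This procedure will be employed for a maximum of two performance subtests". Beyond the tolerance, "If more than 25% of the items within any performance subtest are missing, the entire subtest is missing".

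For the total, which sums eight performance subtests and three examiner ratings, two conditions for having no score are: "If more than two subscales (either performance subtest or examiner ratings) are missing or more than 2 performance subtests have partial missing data". A third condition is the absence of both word-list subtests, Word Recall and Word Recognition. In all other cases the sum of the available subscales is scaled up by 70 over the maximum attainable on them.

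Two further rules affect the counts. The first links two subtests: "if Word Recognition was not completed for any reason, then Remembering Test Instructions must also be scored as not completed". The second concerns a participant "unable to complete the task for cognitive reasons, the worst possible score for the measure will be assigned"; such a subtest has a score and is not missing.

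ADAS-Cog 11 change to Week 48 is a co-primary endpoint and is tested before CDR-SOB (SAP 4.3.4 and 4.8.3). Efficacy analyses use observed data, with imputation in sensitivity analyses only (SAP 4.3.7).

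**The concern.** A scoring rule for incomplete data should not reward losing more of it. Here a subtest that is at least 75% observed can void the whole assessment, whereas the same subtest left undone counts against a different limit and lets the total through. Nothing in Appendix 2 allows a third partly missing subtest to be treated as a missing subscale and prorated, although a subtest with fewer items observed is treated in exactly that way.

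What is at stake is the loss of usable co-primary assessments. The effect depends on the visit:
- **Post-baseline.** The primary model uses all available in-clinic visits (Weeks 12, 24, 36 and 48), so a voided total costs that visit only.
- **Baseline.** ADAS-Cog is scheduled at the baseline visit and not at screening. Both the change score and the baseline covariate need it, so a voided baseline total could leave the participant with nothing to contribute to the ADAS-Cog model.

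**Working it through.** **Inputs (all SAP Appendix 2).** Eight performance subtests; three examiner ratings; scale maximum 70; item tolerance 25%; limit of two missing subscales; limit of two partly missing performance subtests; Word Recall maximum 10; Commands maximum 5.

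**Step 1. The plan's own figure.** With Word Recall and Commands missing, 70/(70 − (10 + 5)) = 70/55 = 1.27. This reproduces. The SAP thus accepts a total with 15/70 = 21% of the scale wholly unobserved.

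**Step 2. The rule as written.** Let m be the number of missing subscales (including Remembering Test Instructions whenever Word Recognition is missing) and p the number of partly missing performance subtests. A total exists if m ≤ 2 and p ≤ 2, and Word Recall and Word Recognition are not both missing.

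**Step 3. Compare two records.**
- Record A: three subtests partly missing, all else complete. p = 3 > 2, so there is no total.
- Record B: Record A with one of the three not done. p is at most 2, and m = 1 (2 if the lost subtest is Word Recognition). There is a total. The scaling ratio is 70/65 = 1.077 if Commands is lost and 70/60 = 1.167 if Word Recall is lost.

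**Step 4. Is this general?** There are C(8,3) = 56 triples and three choices of the lost subtest, so 56 × 3 = 168 cases. Record A is void and Record B is scored in all 168. Leaving out Remembering Test Instructions, which is scored from Word Recognition, gives 35 × 3 = 105 cases, again all of them. With two of the three undone, 132 of 168 are still scored. The 36 failures are Word Recognition paired with any of the six subtests other than Remembering Test Instructions, times six choices of the partly missing one; the linked subtest makes m = 3.

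**Step 5. When one missing item makes a subtest partial.** One missing item out of k is within tolerance if 1/k ≤ 0.25, that is k ≥ 4. With k = 3 it is 33% and the whole subtest is missing. The documents give no item counts.

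**Step 6. Check of the proposed limit**, m + max(0, p − 2) ≤ 2, keeping the Word Recall and Word Recognition condition:

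| p | m | Current rule | Combined count | Proposed rule |
|---|---|---|---|---|
| 2 | 1 | total | 1 | total |
| 2 | 2 | total* | 2 | total* |
| 3 | 0 | none | 1 | total |
| 3 | 1 | none | 2 | total |
| 4 | 0 | none | 2 | total |
| 3 | 2 | none | 3 | none |
| 4 | 1 | none | 3 | none |
| 5 | 0 | none | 3 | none |

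*Unless Word Recall and Word Recognition are both missing.

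When p ≤ 2 the combined count is just m, so every total valid now stays valid. When a partly missing subtest becomes wholly missing, m rises by 1 and p falls by 1. The count is then unchanged if p was 3 or more, and rises by 1 if p was 1 or 2. It never falls, so further loss cannot rescue a void total. The one qualification is the worst-score rule for cognitive reasons: it assigns a score, so such a subtest leaves both counts under the current and the proposed rule alike.

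**The case against.** The literal reading is hard to dispute; the serious objections concern size and intent.

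**Rarity.** The trigger needs three subtests in one session, each with a small gap. Raters are trained and certified (protocol 13.3), and failure for cognitive reasons is scored rather than left missing. This stands: the pattern is probably uncommon.

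**Deliberate quality screen.** Scattered gaps might signal a badly run session, while an undone subtest carries a coded reason. Appendix 3 uses the same two-subtest cap on item proration, which suggests a convention. But the SAP states no such rationale, and it fits poorly with a rule that accepts 15 of 70 points wholly missing. Appendix 3 also has no clause that voids its composite for partly missing subtests.

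**Stronger readings that do not hold.**
- A reader might infer that each lost Week 48 total removes one of the roughly 124 participants per arm assumed in the power calculation. It does not: the participant's Week 12, 24 and 36 totals remain in the repeated-measures model.
- A reader might infer that the rule keeps noisier scores than it discards. The documents give no item weights or variances from which to show this.
- A reader might take it that any three single missing items void the total. This holds only where each affected subtest has four or more items.

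**Simply deleting the partial limit would go too far.** Two missing subscales plus six partly missing subtests would then be scored. This stands, and is why the fix below keeps a limit.

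**Conclusion.** The point holds as a logical fault in the scoring rule for a co-primary endpoint: in every combination checked, the record with less data is scored and the one with more is not. The conclusion rests on reading partly missing and wholly missing as different states, which is how Appendix 2 uses them, and on subtests with at least four items.

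The effect on the trial result cannot be quantified, because the documents give no rate for the pattern; it is probably small. No loss of power and no bias is shown. The most costly single case is a voided baseline total. It is worth correcting because the correction is simple and can be made before lock.

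**What to change.** Amend SAP Appendix 2 before database lock, while the team is blinded:

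1. Apply item-level proration to every performance subtest with 25% or fewer items missing, and delete "This procedure will be employed for a maximum of two performance subtests".
2. In the total-score paragraph, replace the separate limit on partly missing subtests with one combined limit. Suggested wording: *Count the missing subscales and add one for each partly missing performance subtest (some, but no more than 25%, of items missing) beyond the second. If this count exceeds two, the total is missing. The added counts decide validity only; a partly missing subtest keeps its prorated score and stays in the denominator of the prorating ratio.*
3. Keep the condition on Word Recall and Word Recognition, the link to Remembering Test Instructions and the worst-score rule as they are.

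The cost is a small change to the scoring program and its validation, and a few more totals that depend on item-level proration. No new data are needed.
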